and slowly titrated up to maintenance dose. Gabapentin has been used successfully to treat neuropathic pain and perioperative pain ¹³. It has been shown to reduce stroke size, decrease the cortical spreading depression (CSD), which in turn can cause vasospasm and delayed ischemic neurologic deficit (DIND) ¹⁴. Mayo Clinic Jacksonville has been using gabapentin in order to reduce the narcotic requirement and complication. In our retrospective chart review in neurocritical care ICU (NICU) from January 2011 till February 2013, study (53 patients) there was 6% nausea (intolerable in 1.9%) but no major adverse effects of gabapentin maintenance dose (1800-2700mg /day). We also found a decrease in mean use of opioids with the use of gabapentin within the first 4 days post SAH compared to after 5 days (P = 0.01) . There was no fall, dizziness and abnormal liver function associated with the use of gabapentin. Aseptic meningitis was detected with the analysis of cerebrospinal fluid (CSF) during the second half of the ICU stay. The cost of 300mg of gabapentin was average of 30 times less than intravenous fentanyl 100 mcg. We did not find any other study looking at the use of gabapentin in aSAH patients.

The plan is to conduct a randomized control trial with a total of 20 aSAH patients. 10 aSAH patients admitted in NICU will be assigned to receive gabapentin, and 10 will receive placebo. Both of the groups will receive standard of care for pain control for 7 days.

Hypothesis: “Gabapentin will reduce the pain score and narcotics requirement_among hospitalized aSAH patients compared to placebo alone.”

The primary specific aims and hypothesis of this study are:

1. To compare the narcotic requirements among SAH patients experiencing headache treated with gabapentin or placebo for 7 days.
2. To compare efficacy of gabapentin in reducing the headache numeric pain score (NPS) compared to the non-GBP arm among hospitalized aSAH patients. Both groups are treated by an existing standard of care algorithm with narcotics and NSAIDs.

The secondary aims of this study are:

1. To evaluate the initial dose, escalation and side effects of gabapentin (nausea, vomiting, fall, lightheadedness, dizziness, vertigo, confusion).
2. To evaluate the incidence of delirium, vasospasm, delayed ischemic neurologic deficit (DIND) and seizure among hospitalized aSAH patients.
3. To evaluate the incidence of aseptic meningitis with cerebrospinal fluid (white blood cell and red blood cell ratio).

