4. To evaluate the pain control satisfaction among patients treated with or without gabapentin.

If gabapentin reduces the pain and/or improves pain control satisfaction without major side effects it will be drug of choice for headache among patients with SAH with lower cost benefit ratio by decreasing the narcotic requirement.

3. Research Strategy a. Significance

A.1. Subarachnoid hemorrhage

Subarachnoid hemorrhage is mainly due to rupture of saccular aneurysm. This is often a devastating clinical event with mortality rates that approach 40 percent by one month, as well as substantial neurologic morbidity in SAH survivors. The lifetime cost per person of first strokes occurring in 1990 is estimated to be \$228,030 for SAH. Indirect costs accounted for 58.0% of lifetime costs. Aggregate lifetime cost associated with SAH is estimated to be about \$5.6 billion in the U.S. Acute-care costs incurred in the 2 years following a first stroke accounted for 45.0% of these costs, while long-term ambulatory care accounted for 35.0%, and nursing home costs

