In the present study, we are proposing to use GBP among aSAH headache that are able to verbalize their numeric pain score while they admitted in a neuro intensive care unit. Our study is directly inspired by the previous study of GBP in perioperative and neuropathic pain. To date GBP use in aSAH has not been published. This research would be a landmark study exploring the use of GBP in aSAH headache in a prospective fashion. If GBP reduces the SAH-mediated neuropathic and inflammatory pain without major side effects, it could lead to an orphan-drug development extra-murally funded NIH (RO1) or NINDS-funded award to study this drug since SAH disease occurs less than 200,000 cases per year. Therefore, this study would provide pivotal prospective safety and tolerability data as well as some exploratory data on its neuroprotective effects (albeit underpowered). The potential of this study is that if our hypothesis is confirmed that GBP reduces narcotic requirements after SAH, it may become (under FDA-IND development or orphan drug funding) the drug of choice this disease. Further, if the study is positive in terms of its findings for reduced pain and/or neuroprotective effects, this could lead to further drug-discovery for the use of GBP or similar drug design for neuroprotection.

C. Approach

C.1. Preliminary Studies

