C.1.a. Subarachnoid Research: Mayo Clinic Florida (MCF) is a high-volume SAH referral center with an average of about 90 SAH patients a year making this an ideal study population and site to conduct the research study. MCF has a prospective cerebrovascular database of SAH patients that is kept by 3 full-time Neuroscience research coordinators. MCF would be an ideal place to start the GBP study since our center has an existing IRB approval and retrospective study that has shown safety and tolerability of this agent as part of standard management (IRB 13-003673)⁴¹. The purpose of this study is to provide more prospective scientific study to see if the results fit the retrospective data, and possibly help with a larger extra-murally funded trial examining this drug. MCF has a team of experienced neurologists, and intensivists, as well as research coordinator in order to conduct this project. Other trials conducted at MCF in the NeuroICU include CLEAR3 (NCT00784134), ATACH2 (NCT01176565) that are NIH/NINDS funded national/international trials. [name] as the mentor of this study has extensive clinical experience in SAH patients, and has significant research experience in SAH and neurocritical care. He has served as site principal investigator of the aforementioned multicenter research trials at MCF, and is a productive mentor with mentees being academically productive with research abstracts and full-length publications. [name] also holds a FDA-investigational new drug (IND) for nicardipine for SAH, and has experience with this process with the FDA. Similarly [name] has been involved in multiple NIH/NINDS. He have received CREST-2, The National Institute of Neurological Disorders and Stroke which will begin enrolling 2,480 patients in 120 centers in the United States and Canada with carotid disease.

C.1.b. Gabapentin for headache in SAH Research: Our research group at MCF conducted a retrospective study of a consecutive series of SAH patient from January 2011 till February of 2013 in the neurointensive care unit⁴¹. The study had 53 aSAH patients who were treated with GBP along with standard of care analgesics, NSAIDs and sometimes dexamethasone for severe headache. Severe headache was observed in all aSAH patients, with average maximal

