intensity on day 5 of aSAH. GBP dosing was rapidly escalated within days of SAH up to a median of 1200 mg/day, with a range of 300 mg three times a day to 900 mg three times a day which was overall well-tolerated. Approximately 6% of patients treated with GBP had nausea (95% CI, 1-16%) that is also associated with SAH disease. Only 1 patient (1.8%) had to discontinue GBP due to nausea and vomiting. GBP dose was rapidly weaned similar to its tiered dose escalation or stopped after discharge in most of the patients. There were no major reported GBP withdrawal side effects such as seizure. However approximately, 4 patients had return of headaches observed after they weaned off the medication within a 30 day period in which case, GBP was resumed until headaches resolved. In 2 of these cases GBP was used for their outpatient management of baseline migraines or postoperative craniotomy headaches. In the Mayo Clinic study, visual analog scale (VAS) was used which is similar to NPS and was charted on a daily basis to document pain severity. VAS in these patients showed a slow rise from day one of aSAH until a maximum intensity around day 5. Two different peaks on day 11 and day 16 after aSAH were also noted subsequently. These peaks in VAS score also interestingly correlated with high CSF WBC/ RBC ratio and there were no culture proven bacterial or viral infection. This data suggests the inflammatory delayed headache pathophysiology of SAH headache and separate from the initial headache onset. These headaches also were more responsive to corticosteroids apparently since steroid use for breakthrough pain was noted during this time period. This data provides important insight that this period of time of post-SAH headache and meningismus may be a form of inflammatory or steroid- responsive aseptic meningitis.

Overall, the Mayo Clinic study demonstrated that GBP is safe and tolerable in aSAH patients with headache. No major adverse events (AE) were noted. A small portion of patients reported nausea that is inherent to SAH disease, and was managed conservatively with typical anti-nausea medications and did not require GBP discontinuation. The escalation of GBP in this population also appeared feasible and without major side effects. We saw decrease trends in use of opioid and steroids requirements with upward titrated and therapeutic doses of GBP.

C.2. Current Proposal Overview

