Gabapentin escalation dosing will be modeled after our retrospective safety study. We will start with 100 mg orally three times a day then every 24 hours increase to 300 mg tid as tolerated, then 600 mg tid and to a maximum of 900 mg tid. We plan to use 100mg tid then 200 mg tid and 400mg tid if creatinine clearance of 30 -59. We will exclude any patients who have CrCl <30. We will define maintenance dose of GBP as a dose in which after being on it for 24 hours there is 50% reduction of daily average NPS. We will continue maintenance dose throughout hospital stay. aSAH patients will be in observation in NICU for median of 15 days. The placebo will be escalated in the same manner as GBP. A Mayo pharmacist would dispense the study drug (ie., GBP or placebo). Every patients discharged with aSAH will be followed by Mayo neurologist as a SOC and they will plan to reduce or stop GBP.

C.6. Data Analysis

Unless otherwise specified, analyses will be performed using an intention-to-treat approach whereby subjects are analyzed according to randomized treatment arm. The primary endpoint for this trial will be the 7 days of treatment with or without GBP and best medical therapy. For this endpoint the treatment groups will be compared using a two-tailed test with a p -value ≤ 0.05 .

Categorical variables will be summarized as percentages, and continuous factors will be described using means or medians to best describe the distributions. Adverse events will be described as rates, and 95% confidence intervals estimated for those rates. The calculated total daily NPS score; opioid requirement and GBP dose will be analyzed. CSF WBC/RBC ratio will be calculated from the available sample and trended on days of SAH. All the plotted data will be projected with a 95% confidence interval.

We will compare the NPS, patient satisfaction score and the fentanyl requirement among the GBP and placebo group. We will use 2 sample t test or Wilcoxon rank sum test. The data will be analyzed to see if there is difference in incidence of aseptic meningitis, vasospasm and DIND between the GBP and placebo group. If there is difference more than 5 %, we will use regression modeling to analyze the data.

C.7. Sample Size Considerations

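### The aims call gabapentin the future drug of choice and section B calls the safety data pivotal, but 10 gabapentin patients compared only with placebo can support neither statement

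*Combined protocol and SAP*

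**What the plan says.** All references are to the combined protocol and SAP.

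- Section 2, after the list of aims: "If gabapentin reduces the pain and/or improves pain control satisfaction without major side effects it will be drug of choice for headache".
- Section B (Innovation): "this study would provide pivotal prospective safety and tolerability data". The remark in the same sentence about being underpowered is attached to the exploratory neuroprotective data, not to safety.
- Section 2 also gives the size: "10 aSAH patients admitted in NICU will be assigned to receive gabapentin, and 10 will receive placebo". Both groups receive standard-of-care pain control for 7 days.
- Section C.6: "Adverse events will be described as rates, and 95% confidence intervals estimated for those rates". The method for these intervals is not named. C.6 names between-group comparisons for pain score, satisfaction, fentanyl requirement, aseptic meningitis, vasospasm and DIND, but not for adverse events.
- Section C.1.b, on the earlier retrospective series: "The study had 53 aSAH patients who were treated with GBP"; no major adverse events were noted; and "Approximately 6% of patients treated with GBP had nausea (95% CI, 1-16%) that is also associated with SAH disease".
- Softer wording stands elsewhere. Section B says that gabapentin may become the drug of choice under further regulatory development or orphan-drug funding. Section C.1.a says that the study may help towards a larger, externally funded trial.

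**The concern.** The condition in section 2 is "without major side effects". The plan does not define a major side effect, sets no rate that would be tolerated, and bases the sample size in C.7 on pain and satisfaction only. A trial with 10 exposed patients can easily show no major event when the true rate is clinically important, so meeting the condition says little.

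The words drug of choice also imply a ranking against other analgesics. Both arms receive the same standard-of-care ladder (C.2), and the randomised contrast is gabapentin against placebo on top of it. That can show an added benefit, but it cannot rank gabapentin against any alternative.

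Finally, C.1.b notes that nausea also comes with the haemorrhage itself. The comparison that helps to separate drug from disease is the one between the blinded arms, and C.6 does not ask for it.

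At stake is what the report may conclude. Written to match section 2, it could present a small placebo-controlled study as settling both safety and choice of treatment.

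**Working it through.** **Inputs.** 10 patients per arm (section 2); 95% intervals for adverse event rates (C.6), taken as two-sided; 53 patients with no major adverse events and about 6% nausea, interval 1 to 16% (C.1.b). Zero events in 10 is a hypothetical best case, since the plan states no expected rate of major events.

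**1. Reproduce the plan's own interval.** Six percent of 53 implies 3 patients (inferred; 3/53 = 5.7%). The exact (Clopper-Pearson) limits are the 2.5% quantile of Beta(3, 51) and the 97.5% quantile of Beta(4, 50), that is 1.2% and 15.7%. These round to the stated 1 to 16%. The Wilson interval, 1.9% to 15.4%, would round to 2 to 15%. The plan's figure is therefore consistent with the exact method, which is used below.

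**2. Upper limit for no events in 10.**
- Exact, two-sided 95%: 1 − 0.025^(1/10) = 30.8%.
- Exact, one-sided 95%: 1 − 0.05^(1/10) = 25.9%.
- Wilson, two-sided 95%: 27.8%.
- A single event, 1/10, would give an exact interval of 0.3% to 44.5%.

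**3. Chance of seeing no event in 10,** (1 − p)^10:

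| True rate p | P(no event in 10) |
|---|---|
| 1% | 90% |
| 5% | 60% |
| 10% | 35% |
| 20% | 11% |

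**4. Set the retrospective series beside it.** For 0/53 the two-sided exact upper limit is 1 − 0.025^(1/53) = 6.7%. If the true rate were 6.7%, this trial would show no event with probability (1 − 0.067)^10 = 50%. Simple pooling, which the plan does not propose, gives 0/63 and an upper limit of 1 − 0.025^(1/63) = 5.7%. A clean result in 10 patients would thus add little precision. What the trial adds is a concurrent, blinded placebo arm.

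**5. Numbers for scale.** With no events observed, a two-sided exact upper limit of 10% or less needs at least ln(0.025)/ln(0.90) = 35.01 exposed patients, so 36. For 5% or less the same formula gives 72.

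**6. Between-arm contrast.** With 0/10 in both arms, the Newcombe interval for the risk difference combines the two Wilson limits. Each Wilson upper limit is 27.8%, so the interval is 0 ± √(0² + 0.278²), about ±28 percentage points.

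**7. Are the data there?** C.4 plans daily documentation of side effects for gabapentin and placebo and reporting in both groups by the NIH adverse event classification. Table 2 in Appendix 1 has a column for each arm. Of the seven side effects in secondary aim 1, nausea, vomiting and dizziness have rows in Table 2. Fall, lightheadedness, vertigo and confusion do not.

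**The case against.** Several points on the other side are sound.

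- A reader might infer that section 2 sets a decision rule under which a clean safety result leads directly to a practice conclusion. The documents do not support that. The sentence is a closing statement of significance in the aims, it also requires a benefit on pain or satisfaction, and C.6 contains no safety criterion and no conclusion triggered by zero events.
- A reader might infer that the sponsor sees no need for further study. Sections B and C.1.a say otherwise. The surviving point is a conflict between one sentence in section 2, one adjective in section B, and the plan's own more cautious wording.
- A reader might infer that adverse events could not be related to the drug at all because only per-arm rates are planned. That goes too far. Events are recorded in both blinded arms, and the remark on nausea describes the earlier uncontrolled series. What stands is that C.6 names no between-arm contrast for them.
- C.6 already plans 95% intervals, so 0/10 would be reported with a wide upper limit and not as a bare absence of events. This stands, but the condition in section 2 does not refer to those intervals.
- Taking 31% as the whole state of knowledge would ignore the 53 earlier patients. At a true major event rate of 10%, none in 53 would have probability 0.9^53, about 0.4%. The series therefore has to be cited. It was a retrospective chart review without controls and may have under-recorded events, so it does not establish safety.

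It is also true that any 20-patient trial gives imprecise safety data. That is a reason for modest wording and not a fault in the size of a preliminary study.

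**Conclusion.** The point holds as a mismatch between claim and design. Zero major events among 10 gabapentin patients would exclude only true rates above about 31% (exact, two-sided 95%; 26% one-sided), and a placebo add-on trial cannot rank gabapentin against other analgesics. Neither the drug-of-choice statement nor the word pivotal is supportable.

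This rests on all 10 patients being exposed and observed, on independent events, and on no major event being seen; one event would widen the interval to 0.3% to 44.5%. Open-label gabapentin that placebo patients may receive after day 7 lies outside the blinded comparison and is not counted.

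The change is worth making before the trial reports because it governs what may be concluded. It does not touch the randomisation, sample size, endpoints or primary analysis.

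**What to change.** 1. **Section 2.** Replace the drug-of-choice sentence with a statement that a positive result would support a larger trial, in line with section C.1.a.
2. **Section B.** Replace pivotal with preliminary. State that no major event among 10 gabapentin patients would exclude only rates above about 31% (exact, two-sided 95%), and cite beside it the retrospective 0/53 with its upper limit of 6.7%, noting that the series was uncontrolled.
3. **Section C.6.** Name the exact method for the per-arm 95% intervals. Beside them, add the gabapentin-minus-placebo risk difference with a 95% interval (for example Newcombe) for major adverse events and for each side effect in secondary aim 1. Label these as description and not as tests.
4. **To make item 3 workable.** Define a major adverse event in terms of the classification that C.4 already adopts, and add rows to Table 2 for fall, lightheadedness, vertigo and confusion.

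The cost is a few sentences, a definition, four form rows and one column in the safety table. No new visits or assessments are needed. The downside is a more modest claim and wide intervals, about ±28 percentage points where neither arm has an event.

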This study will be a randomized, placebo-controlled clinical trial enrolling 20 subjects at MCF to either GBP + standard of care (SOC) vs placebo + SOC arm. While enrolling the patients we will stratify patients via numerical pain score (NPS) to either <5 or ≥ 5 . Patients with an NPS ≥ 5 will be randomly assigned to either GBP or placebo group within 72 hours of SAH admission and after informed consent. The SOC pain regimen is comprised of intravenous (IV) fentanyl 25mcg to 50mcg q1hr PRN for head and neck pain as the first-line agent. If SAH pain remains >5 on NPS after the next nursing pain assessment, the next tier of pain agents will be utilized consisting of the following tier:

2nd line- enteral /PO oxycodone 5mg PRN q4hrs pain, and if still in pain after next assessment, then 10mg q4hrs PRN,

3rd line (if 2nd line failed to reduce NPS < 5)- IV 15mg ketorolac q6hrs PRN x 24hrs, unless serum creatinine > 1.3 , or GFR < 30 , or concern for gastrointestinal bleed risk, or history of bleeding peptic ulcer.

4th line (if 3rd line failed to reduce NPS < 5)- dexamethasone 2mg IV BID x 24hrs.

The patient will be enrolled within 72 hours of admission and meeting inclusion criteria by investigator and coinvestigators. Documentation of numeric pain score will be done by standard of care per nursing and hospital policies in the medical record. After consent and enrollment, a data collection sheet will be recorded by nursing to summate the NPS scores every 24 hours along with the SOC pain management plan. The SOC pain management plan will be implemented by the NeuroICU team of residents, attending, and nurse practitioners/PA's who are available on a 24/7 basis. A decrease in pain score equal or more than 50% will be defined as meeting the goal of the study, and as headache pain being under control. Patients will begin study medication (gabapentin or placebo) at approximately 9:00 AM on the morning following randomization into the trial to allow for documentation of the baseline average NPS. The

baseline NPS will be used to determine if the patient has had a 50% or more decrease in pain score.

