2. Have aneurysmal SAH diagnosed by CT scan of the brain and/or angiogram evidence of intracranial aneurysm (CTA or digital subtraction angiogram or MRA)
3. Have symptomatic headache
4. Able to swallow and verbalize pain score
5. No known allergy to GBP or fentanyl
6. Numeric pain score \geq 5
7. Ability to provide written personal consent

Exclusion Criteria:

1. GBP use prior to SAH admission
2. Renal failure with creatinine clearance less than 30 ml/min
3. Unable to receive standard of care pain medications
4. Pregnant patients
5. History of severe depression defined by DSM IV

C.4. Study Procedures & Schedule

All study medication will be labeled and dispensed according to subject number ensuring that treatment assignment remains concealed to the subject, investigator, and all study personnel who have subject contact. Data collection will be done in case report form at the bedside and

later will be enter in spread sheet. We will issue unique ID for each study patients. 20 preprinted study ID labels will be used to randomly select study patients.

Subject selection: All aneurysmal SAH admitted will be screened by the Mayo Cerebrovascular laboratory for eligibility and the NeuroICU attending and/or fellow will be contacted about potential enrollment in the study. Subjects who are able to provide written consent will be approached for enrollment. Based on prior volumes, we expect to have 20 subjects enrolled within 6-9 months.

Pain assessment: We will use numeric pain scale (NPS) that is been validated in many studies and is easy to use. Nurse and medical staff are familiar with this scale in our institute as it has been commonly used as standard of care. We plan to perform this pain scale every 4 hours in the study patients. The scale range from 0-10, 0 being the no pain and 10 being the worst pain ever. We will calculate daily total score for each patient. Only headache and neck pain will be included in the study to calculate the pain score. We will not include the score for other pain like back and abdominal pain.

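### The NPS <5 / ≥5 split in C.2 is a screening step that balances nothing among the 20 randomised patients, and C.6 has no baseline-adjusted NPS comparison

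*Combined protocol and SAP*

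**What the plan says.** **Enrolment and allocation.** C.2 (Current Proposal Overview) states: "While enrolling the patients we will stratify patients via numerical pain score (NPS) to either" <5 or ≥5. The sentence after it reads: "Patients with an NPS ≥ 5 will be randomly assigned to either GBP or placebo group". Inclusion criterion 6 in C.3 sets the same threshold of 5, and C.2 ties enrolment to eligibility: "The patient will be enrolled within 72 hours of admission and meeting inclusion criteria by investigator and coinvestigators". C.4 describes 20 preprinted ID labels as the selection device. No separate lists by pain score, other stratification factor, blocking or minimisation is described.

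**Baseline pain.** C.2 holds the first dose until the morning after randomisation so that a baseline average NPS can be documented. That value is the reference for a decrease of 50% or more, which C.2 calls the goal of the study. The 50% reduction also defines the maintenance dose in C.2 and C.5.

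**Analysis.** For NPS, satisfaction and fentanyl requirement, C.6 says: "We will use 2 sample t test or Wilcoxon rank sum test". It names no baseline covariate, change from baseline or between-arm comparison of 50% responders. The one mention of regression follows the sentence on aseptic meningitis, vasospasm and DIND, depends on a difference above 5%, and lists no covariates.

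**The concern.** A reader who meets the word stratify in C.2 will assume that the design balances baseline pain between arms. It cannot, because the factor takes a single value in everyone randomised. The other usual way to deal with baseline pain is adjustment in the analysis. C.6 does not provide it, although the protocol delays dosing to obtain the value that adjustment would need.

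With 10 patients per arm, two things are at stake. One is precision that could be had from data already collected. The other is interpretation: if the arms differ visibly in baseline pain and no adjustment was pre-specified, the reader is left with an unadjusted result or a post hoc adjusted one.

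**Working it through.** The plan gives no figure for baseline balance or for the correlation between baseline and later pain, so there is none to reproduce. The sample-size statement in C.7 plays no part in what follows.

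**1. The factor is constant.** C.2 randomises only NPS ≥5, criterion 6 admits only NPS ≥5, and enrolment requires the criteria to be met. The number of randomised patients in the <5 group is therefore 0 of 20. A factor with one level cannot balance scores within the range 5 to 10.

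**2. Chance imbalance with 10 per arm** (C.7 and Specific Aims). The difference in baseline means has standard error SD × √(2/10) = 0.447 SD. Then

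2 × P(Z > 0.5 / 0.447) = 2 × P(Z > 1.118) = 26.4%.

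To put this in points, a distribution has to be assumed. Simulated whole scores on 5 to 10, with 10 against 10, give these chances of a difference of at least 1 point:

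- uniform, SD 1.71: 22%
- skewed to high scores, SD 1.58: 18%
- more strongly skewed, SD 1.40: 13%

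**3. What such a gap does to the outcome.** A baseline gap of 0.5 SD moves the expected outcome difference by r × 0.5 SD, where r is the baseline-outcome correlation. At an assumed r = 0.5 that is 0.25 SD.

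**4. What adjustment is worth at N = 20.** In large samples, ANCOVA multiplies the variance of the treatment difference by 1 − r². Estimating the slope from 20 patients in two arms multiplies it again by about 1 + 1/(N − 4) = 1 + 1/16 = 17/16 (normally distributed covariate). The equivalent number of unadjusted patients is 20 / [(1 − r²) × 17/16]. All values of r are assumed.

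| r | 1 − r² | × 17/16 | Equivalent total |
|---|---|---|---|
| 0.1 | 0.99 | 1.052 | 19.0 |
| 0.2 | 0.96 | 1.020 | 19.6 |
| 0.3 | 0.91 | 0.967 | 20.7 |
| 0.5 | 0.75 | 0.797 | 25.1 |
| 0.7 | 0.51 | 0.542 | 36.9 |

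Break-even is where (1 − r²) × 17/16 = 1, so r² = 1/17 and r ≈ 0.24.

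**5. Is the baseline a valid covariate?** It is recorded after randomisation, but before the first dose and, under C.4, with assignment concealed from the subject and from study personnel in contact with the subject. Treatment cannot have affected it.

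**The case against.** The strongest reply is that the C.2 sentence is only loosely worded. Read with the next sentence, it most naturally describes sorting at enrolment, and no stratified list appears anywhere. That stands. A reader might infer that a stratified randomisation was planned and is broken; the documents do not show that one was planned. Correcting the sentence changes nothing in the conduct of the trial, only what the reader believes the design achieves.

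Second, randomisation protects the unadjusted test, and this also stands. The t or Wilcoxon test is valid and already allows for chance imbalance, so there is neither bias nor inflation of type I error.

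Third, the gain may be small. Entry is truncated at 5, rescue tiers in C.2 respond to an absolute pain level and so compress later scores, and C.1.b reports pain rising until about day 5, after the 72-hour enrolment window. All three could lower r. This is fair: at r = 0.3 the gain is under one patient, and below about 0.24 there is a loss. The loss is bounded, however. Even at r = 0.1, 20 adjusted patients are worth 19.0 unadjusted ones, against 25.1 at r = 0.5.

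Fourth, ANCOVA of NPS does nothing for the narcotic requirement, which is primary aim 1. That limit is accepted.

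**Conclusion.** The point holds as one of wording and efficiency. The split at 5 gives no baseline balance among the 20 randomised patients, and C.6 contains no baseline-adjusted NPS comparison although the baseline is collected. The 26% chance of a gap above 0.5 SD rests on 10 per arm and a normal approximation. The equivalents of 20.7, 25.1 and 36.9 patients rest on assumed correlations of 0.3, 0.5 and 0.7 and on the 17/16 factor; the documents supply no correlation.

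Three stronger conclusions are tempting and not supported:

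- **That baseline pain is not controlled at all.** Entry is restricted to NPS ≥5 and allocation is random.
- **That the protocol ignores baseline.** It is the reference for the 50% decrease that C.2 calls the study goal. What is missing is its use in the C.6 comparison.
- **That chance imbalance is large relative to the effect sought.** C.7 gives 25% without a reference mean and an SD of 5.84 without saying whether it belongs to a 0-10 average or a 24-hour total, so the comparison cannot be made.

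**What to change.** **C.2:** call the <5 / ≥5 split a screening step, or delete the sentence.

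**C.6:** pre-specify an ANCOVA of the NPS outcome on treatment arm, with baseline average NPS as covariate, and keep the Wilcoxon rank sum test as a sensitivity analysis. The NPS outcome has to be named for this. At present C.6 identifies the primary endpoint only as the 7 days of treatment. The mean of the daily average NPS over those 7 days would be one workable summary, with outcome and baseline on the same scale.

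**Cost:** wording in two sections and one degree of freedom (residual 17 instead of 18), with no new data, visits or patients. If the correlation proves very low, there is a slight loss of precision. The narcotic-requirement comparison needs its own specification and is not addressed by this change.
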